10.1.5 Collection of immunologic blood samples

For the BCG alone arm:

- at week 0 or at randomization by 1 10cc purple top tube
- prior to treatment at weeks 3 and 8 by 2 10cc red top tubes and 6 10cc green top tubes
- at the end of study (between weeks 17-20) by 1 10cc purple top tube, 2 10cc red top tubes and 6 10cc green top tubes.

For the BCG + PANVAC vaccine arm:

- at week 0 by 1 10cc purple top tube

- prior to treatment at weeks 0, 3, 8, 11, and 15 by 2 10cc red top tubes and 6 10cc green top tubes
- at the end of study (between weeks 17-20) by 1 10cc purple top tube, 2 10cc red top tubes and 6 10cc green top tubes.

Additionally, blood may be collected on follow-up visits for up to 12 months following end of study cystoscopy/ bladder biopsy. From this blood, PBMCs and sera will be isolated, when appropriate samples are available, for the following immune correlates:

Immunologic testing will include:

1. Circulating Tumor Cytokines (CTC) analysis
2. IFN-gamma ELISPOT assays for CD8 T-cell responses specific for CEA, MUC-1, and Brachyury (Limited to patients with HLA-A2 allele)
3. Measure CD4 antigen-specific response to CEA
4. Sera samples will be analyzed for the development of antibodies to CEA, MUC-1 and Brachyury. (Samples from baseline and at end of study)
5. Flow cytometry analysis using 10 markers of all PBMC samples for each of the following cell types: CD4, CD8, Tregs, MDSCs, and NK.
6. Serum for NCA (CEA-CAM) titers will be drawn anytime that a patient exhibits new onset neutropenia (ANC <1000)
7. Immunologic studies will be repeated more frequently if clinically indicated, and any abnormalities potentially related to treatment will be followed until they have resolved, or have been determined to not be treatment-related or until the participant's primary medical care is transferred from the principal investigator.

10.1.6 The immunologic testing samples for CTC analysis will be processed at:

[name] Lab
[name]
[name]

For patients at CINJ, research samples consisting of 2 purple top tubes (week 0 and week 17-20) will be drawn. These tubes will be further processed as per Appendix E, Section **17.5** and then shipped via Fed-Ex to [name] lab:

[name]
c/o [name] or [name]
Urologic Oncology Branch
[name]
[name]

10.1.7 The other immunologic testing samples will be processed at:

Clinical Services Program
NCI Frederick Cancer Research and Development Center
[name]

10.1.7.1 Biopsies

Biopsies will be obtained at the end of therapy solely for diagnostic purposes as per standard of care to ensure that cancer is no longer present. After pathologic diagnosis, each biopsy specimen will be further analyzed by immunohistochemistry for the following: (a) expression of CEA and MUC-1 antigens on tumor cells, (b) the presence of CD4 and CD8 T cells, (c) the presence of regulatory T cells (Tregs) by double staining with FoxP3 and CD4, and (d) the presence of myeloid derived suppressor cells (MDSC).

Satisfactory analytical performance characteristics (specificity, sensitivity and reproducibility at the minimum) of individual antibodies or affinity ligands for use in immunohistochemistry will be demonstrated prior to analyses of glycosylated CEA and MUC-1 on tumor cells, CD4 and CD8 T cells, Tregs by double staining with FoxP3 and CD4, and MDSC.

10.1.7.2 PBMCs, sera, and urine

The following time points will be analyzed: baseline (prior to vaccination in vaccination arm), week 3 (prior to BCG for both arms), week 8 (prior to last BCG for both arms), and at end of study (between weeks 17-20).

PBMCs

All patients who have the HLA-A2 allele will be analyzed by ELISPOT for CD8 T-cell responses specific for CEA, MUC-1, and a cascade antigen Brachyury. All samples will be evaluated for CD4 responses specific for CEA protein. All immune assays will have appropriate antigen controls. All PBMC samples will be analyzed by flow cytometry using 10 markers for each of the following cell types: CD4, CD8, Tregs, MDSCs, and NK.

- Satisfactory analytical performance characteristics of individual antibodies or affinity ligands for use in ELISPOT, flow cytometry, or ELISA will be demonstrated prior to analyses of the proposed protein markers, cytokines and chemokines.
- Analyses of sera samples for quantitation of antibodies to CEA, MUC-1 and a cascade antigen Brachyury will be described in detail to show clinically recapitulated tumor-associated antigens, including glycosylated proteins, are used in measuring autoantibodies in sera.

Background: Our studies in the LTIB have demonstrated the ELISPOT assay for IFN- γ production to be quantitative and reproducible as a measure of human T-cell responses to vaccination (26). The continued use of one reproducible assay has been instrumental in our ability to evaluate and compare patients' immune responses using different vaccines and vaccine strategies in the same institution, and among different cancer centers. ELISPOT assays employing the CEA agonist peptide and the MUC-1 agonist peptide have already been developed.

Sera

Sera samples at all time points will be analyzed for the development of antibodies to CEA, MUC-1, and a cascade antigen Brachyury.

Urine

Urine samples may be collected at baseline and at the end of therapy (week 17-20) for the presence of cytokines and chemokines. In addition, an effort will be made to collect urine at the time of BCG instillation #1 and #3 to assess for cytokine production in response to BCG therapy (as described earlier in section **10.1.2** and in Section **17.5** (Appendix E)).

For patients at CINJ, research samples consisting of urine (week 0, week 3, week 5, and week 17-20) will be drawn. These tubes will be further processed as per Appendix E, Section **17.5** and then shipped via Fed-Ex to [name] lab:

[name]
c/o [name] or [name]
Urologic Oncology Branch
[name]
[name]

Bladder cancer is believed to be an immune-modulated malignancy and therefore the immune correlates will be used to establish whether or not there is an immune basis for bladder cancer. If tumors are found to have a certain proportion of immune subsets, then the correlates may be used as potential markers of disease in the future.

10.2 SAMPLE STORAGE, TRACKING AND DISPOSITION

All specimens obtained for research purposes will be coded upon arrival in the UOB research laboratory to maintain patient confidentiality. All samples will be accessioned and entered into a database (such as LabMatrix) with access limited to the PI and UOB research data managers. The location of all samples will be carefully tracked in the database. All stored samples will be coded and identifying patient information will not be placed on sample containers. Stored samples will be kept in freezers/refrigerators or secure containers located in the Urologic Oncology Branch research laboratories or in approved storage facilities. The research samples collected will be used for the correlative/biomarker studies mentioned above in Section 10.1. Tissue slides/blocks may be obtained in order to determine protocol eligibility. Tissues are submitted to the NCI Laboratory of Pathology at the NIH Clinical Center for clinical determination of histologic features. Specialized stains/assays may be used to clarify tissue phenotype. After completion of analysis, tissue slides/blocks are either returned to the originating pathology department or archived in the Laboratory of Pathology or Urologic Oncology Branch and tracked in the UOB database (LabMatrix). Archived material will be retained for the duration of the study unless the originating pathology department requests return.

Coded/anonymous samples with minimal clinical information may be shared with qualified NIH and non-NIH researchers who have IRB-approved protocols with similar research objectives. No personal identifying information such as name, address, or date of birth will be provided to the non-UOB investigator. In the event a subject is eligible to participate in a clinical trial based on tumor characteristics, coded tissue samples may be sent to an outside laboratory. Samples will be ordered and tracked through CRIS Screens. Should a CRIS screen not be available, the NIH form 2803-1 will be completed and will accompany the specimen and be filed in the medical records. Samples will not be sent outside the NIH without IRB notification and an executed MTA.

Subjects will be given the option of consenting to current and future use of their research samples per the informed consent process with their option declared in the consent document. Samples will be destroyed at the completion of the study on those subjects who decline future use of their samples. Otherwise, any specimens that are remaining at the completion of the protocol will be stored for an indefinite amount of time. These specimens may be banked and used in the future to investigate new scientific questions related to this study. However, this research may only be done if the risks of any new questions were covered in the consent document and protocol. Any new uses of the samples other than those defined in this protocol will be submitted prospectively for IRB review and approval. The IRB will be notified in the event research samples are inadvertently lost or destroyed and meet the criteria in section 7.2.1.

10.2.1 Storage and Tracking of Collected Blood Samples

All data associated with the patient samples is protected by using a secure database. All samples drawn at the NIH Clinical Center will be stored in the laboratories of the Urologic Oncology Branch as previously described.

Serum samples will be stored in -80°C freezers and PBMC samples will be stored in vapor phase liquid nitrogen at the NCI Frederick Central Repository in Frederick, MD. Samples drawn at the NIH Clinical Center will be transported by the Leidos couriers; samples from CINJ will be sent via Fed-Ex, as previously described.

Samples will be tracked and managed by the Central Repository database. Leidos Biomedical Research, Inc. manages the NCI Frederick Central Repositories. NCI Frederick Central Repositories store, among other things, biological specimens in support of NIH clinical studies. All specimens are stored in secure, limited access facilities with sufficient security, back-up and emergency support capability and monitoring to ensure long-term integrity of the specimens for research.

Sample data is stored in the BioSpecimen Inventory (BSI) System II. This inventory tracking system is used to manage the storage and retrieval of specimens as well as maintain specimen data. BSI is designed for controlled, concurrent access. It provides a real-time, multi-user environment for tracking millions of specimens. The system controls how and in what order database updates and searches are performed. This control prevents deadlocks and race conditions. For security, BSI has user password access, 3 types of user access levels, and 36 user permissions (levels of access) that can be set to control access to the system functions. BSI provides audit tracking for processes that are done to specimens including shipping, returning to inventory, aliquoting, thawing, additives, and other processes. BSI tracks the ancestry of specimens as they are aliquoted, as well as discrepancies and discrepancy resolution for specimens received by the repository. If a specimen goes out of the inventory, the system maintains data associated with the withdrawal request. Vials are labeled with a unique BSI ID which is printed in both eye-readable and bar-coded format. No patient-specific information is encoded in this ID.

Investigators are granted view, input and withdrawal authority only for their specimens. They may not view specimen data or access specimens for which they have not been authorized. Access to specimen storage is confined to repository staff. Visitors to the repositories are escorted by repository staff at all times.

10.2.2 Protocol Completion/Sample Destruction

Once primary research objectives for the protocol are achieved, intramural researchers can request access to remaining samples providing they have an IRB approved protocol and patient consent.

Samples, and associated data, will be stored permanently unless the patient withdraws consent. Loss or unanticipated destruction of samples will be reported per section **7.2.1**.

11 STUDY CALENDARS

Evaluations below may be performed within \pm 5 days of indicated time in order to accommodate patient schedules, holidays and weather emergencies.

A) STUDY CALENDAR FOR BCG + PANVAC ARM

	Baseline (On study)	Week 0	Week 3	Week 4	Week 5	Week 6	Week 7	Week 8	Week 11	Week 15	Week 17- 20	Follow- up ¹⁰
BCG			X	X	X	X	X	X				
PANVAC-V ¹		X										
PANVAC-F ¹			X				X		X	X		
NIH Advanced Directives Form ¹¹	X											
History and Physical ²	X		X	X	X	X	X	X	X	X	X	X
CBC with differential ³	X										X	X ^o
Chemistry ^{3,4}	X										X	X ^o

Abbreviated Title: Vaccine and BCG for bladder ca

Version Date: 05/22/2025

	Baseline (On study)	Week 0	Week 3	Week 4	Week 5	Week 6	Week 7	Week 8	Week 11	Week 15	Week17- 20	Follow- up ¹⁰
PT, PTT ³	X										X	X ^o
PPD (Research)	X										X	
Urinalysis ⁵	X		X	X	X	X	X	X		X	X	
Urine Cytology ⁶	X										X	X
Urine (Research) ⁷		X	X*		X*						X	X ^o
Immunology (Research blood) ⁸		X	X					X	X	X	X	X ^o
Serum Beta- HCG ⁹	X											
Biopsy											X	X
Chest X-ray	X										X	
CT urogram	X										X	

B) STUDY CALENDAR FOR BCG ONLY ARM

	Baseline (On study)	Week 0	Week 3	Week 4	Week 5	Week 6	Week 7	Week 8	Week 11	Week 15	Week17- 20	Follow- up ¹⁰
BCG			X	X	X	X	X	X				
NIH Advanced Directives Form ¹¹	X											
History and Physical ²	X		X	X	X	X	X	X		X	X	X
CBC with differential ³	X										X	X ^o
Chemistry ^{3,4}	X										X	X ^o
PT, PTT ³	X										X	X ^o
PPD (Research)	X										X	
Urinalysis ⁵	X		X	X	X	X	X	X			X	X

	Baseline (On study)	Week 0	Week 3	Week 4	Week 5	Week 6	Week 7	Week 8	Week 11	Week 15	Week 17- 20	Follow- up ¹⁰
Urine Cytology ⁶	X										X	X
Urine (Research) ⁷			X*		X*						X	X ^o
Immunology (Research blood) ⁸		X	X					X			X	X ^o
Serum Beta- HCG ⁹	X											
Biopsy											X	X
Chest X-ray	X										X	
CT urogram	X										X	

¹ Applies only to treatment arm 2 (BCG + PANVACTM). Panvac administration continues as planned regardless of any delays in BCG administration.

*These time periods should correspond to BCG instillations #1 and #3, respectively. If a postponement of an instillation occurs, urine collection will occur after instillations #1 and #3 irrespective of the trial week. On these weeks, urine will be collected twice: first collection will be prior to BCG instillation and second collection of urine will be 2 hours after drainage of BCG.

² Baseline: H & P and laboratory studies should be completed within 28 days of initiating treatment. This will include determination of ECOG performance status.

³ Baseline laboratory studies should be completed within 28 days of initiating treatment.

⁴ Chemistry panel: Na+, K+, Cl-, CO₂, glucose, BUN, creatinine, albumin, calcium, magnesium, phosphorus, alkaline phosphatase, ALT, AST, total bilirubin, pre-albumin, and LDH.

⁵ Urinalysis: If prior to an operative procedure, then will be obtained within 2-21 days of surgery and with an accompanying urine culture. If prior to BCG administration, a simple urinalysis will be performed in the hospital on the day of administration. ***Urine will be tested weekly prior to each BCG administration and the presence of gross hematuria or a urinary tract infection by urinalysis will result in holding that week's BCG dose as specified in the protocol.

⁶ Urine cytology: will be obtained from voided urine within 2-21 days of operative procedures OR through instrumentation at the time of an operative procedure

⁷ Urine (research): Urine will be obtained for correlative immune studies checking for chemokine and cytokine levels

⁸ Blood will be obtained for immunologic/research assays. CTC analysis, plasma and sera will be isolated to look for CD4 antigen-specific responses, CD8 antigen-specific responses, and flow cytometry profiles of various immune cell types.

⁹ In females of child-bearing age, Beta-HCG to be done at baseline within 48 hours prior to receiving vaccinia

¹⁰ These patients will be followed every 3 months for 1 year after the completion of the initial 20 week study course with standard of care for non-muscle invasive high grade bladder cancer. This includes urinalysis, urine cytology, cystoscopy, possible bladder biopsy, and medical assessments. For patients unable to complete every 3 month follow-up at the NIH or CINJ after week 20, we will keep them on study and obtain their outside pathologic records and labs from their outside urologists who will perform these evaluations.

¹¹ As indicated in section **15.3**, all subjects will be offered the opportunity to complete an NIH advanced directives form. This should be done preferably at baseline but can be done at any time during the study as long as the capacity to do so is retained. The completion of the form is strongly recommended, but is not required. Participating sites should adhere to appropriate procedures specific to their site.

X^o = optional

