5.4 DOSE LIMITING TOXICITY

TICE BCG will be given in the standard dose and schedule as described above. All toxicities observed will be tabulated by maximum grade per subject. A dose limiting toxicity (DLT) will be any grade 3 or greater adverse effect (AE) by CTCAE v5.0 related to the investigational agent and persisting for more than one week and not improving by routine standard of care. In

addition, any grade 3 or greater AE as per a previously published vaccinia toxicity grading scale³³ related to the investigational agent will also be considered a DLT.

Intravesical BCG therapy can lead to common side effects that are usually self-limited, particularly with dose reduction. These side effects include, but are not limited to, gross hematuria, dysuria, frequency, urgency, bladder spasms, and generalized cystitis. These side effects will not be considered a DLT if it is related to BCG and resolves with BCG dose reduction and/or postponing therapy by 1-2 weeks and treating symptoms with conservative management. In contrast, persistent side effects despite dose reduction/postponing of BCG therapy or the development of systemic BCG infection (aka “BCG-osis”) will be considered a DLT.

Severe adverse events due to local instillation of BCG are uncommon. In a retrospective analysis of 2602 patients reported in 1989, the overall rate of serious complications was less than five percent.³⁴ The most common complication was fever >103°F in 2.9 percent followed in decreasing frequency by:

- Significant hematuria (1 percent)
- Granulomatous prostatitis (0.9 percent)
- Pneumonitis and/or hepatitis (0.7 percent)
- Arthralgia (0.5 percent)
- Epididymitis (0.4 percent)
- Sepsis (0.4 percent)
- Rash (0.3 percent)
- Ureteral obstruction (0.3 percent)
- Contracted bladder (0.2 percent)
- Renal abscess (0.1 percent)
- Cytopenia (0.1 percent)

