6.2 PANVAC™-V (VACCINIA) AND PANVAC™-F (FOWLPOX)

6.2.1 Dosing delay

- Subjects must have recovered to \leq grade 1 toxicity related to vaccine for constitutional symptoms (that are not related to the BCG or medications related to BCG treatments) in order to receive a subsequent vaccination. These constitutional symptoms are listed in Section 8.1.1.1.

- Subjects with \leq grade 2 toxicity not related to vaccine treatment (i.e. attributed to BCG) will remain eligible to receive vaccine.
- Subjects that recover from grade 3 toxicity unrelated to vaccine treatment (i.e. related to BCG) will remain eligible for the vaccine. However, subjects that experience a grade 4 toxicity unrelated to vaccine treatment (i.e. attributed to BCG) will not remain eligible for further vaccine administration.
- If BCG is permanently discontinued, the patient will remain eligible for further vaccine administration in the absence of a grade 4 toxicity.
- Vaccination will be held for $>$ grade 2 proteinuria measured initially by a urine dipstick but confirmed by a 24 hour urine collection.
- If \geq grade 2 nonautoimmune toxicity attributable to the vaccine persists for $>$ 42 days, the subject will not receive further vaccine inoculations and will be removed from the protocol treatment and followed for resolution of toxicity and immune endpoints.
- Subjects who develop grade 3 injection site reactions will have their vaccine held until injection site reaction resolves to grade 2 or less.
- Subjects who develop \geq a grade 2 allergic or autoimmune disease that threatens vital organ function or any \geq grade 3 autoimmunity, not related to a therapeutic response, will be removed from the protocol treatment and followed for resolution of toxicity and immune endpoints. Follow-up will be performed during each vaccination and blood draw interval for immunologic testing as described in Section 11
- Subjects who develop any grade 4 toxicity attributable to the study drug(s) will be removed from the protocol treatment and followed for resolution of toxicity and immune endpoints.

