 - Eczema vaccinatum (vaccinia lesion development on areas of the skin that are, or had at one time been, eczematous)
 - Progressive vaccinia (local vaccination lesion fails to heal and develops progressive necrosis, with destruction of large areas of skin, subcutaneous tissue, and underlying structures. Progressive lesions may spread to other skin surfaces and to bone and viscera)
 - Post-vaccinia encephalitis/encephalomyelitis
 - Fetal vaccinia
 - Myocarditis/pericarditis
3. The inclusion of co-stimulatory molecules in these agents may theoretically stimulate autoimmunity or exacerbate existing disease in susceptible individuals.
4. Thrombotic thrombocytopenic purpura (TTP) occurred with closely related agents, PROSTVAC-V/TRICOM [Recombinant Vaccinia-PSA(L155)/TRICOM] and PROSTVAC-F/TRICOM [Recombinant Fowlpox-PSA(L155)/TRICOM].

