Adverse Event	N	Overall (Grade ≥ 3)	Adverse Event	N	Overall (Grade ≥ 3)
Dysuria Urinary	401	60% (11%)	Arthritis/Myalgia	18	3% (<1%)
Frequency Flu-Like Syndrome	272	40% (7%) 33%	Headache/Dizziness	16	2% (0) 2%
Hematuria Fever	224	(9%) 26% (7%)	Urinary Incontinence	16	(0) 2%
Malaise/Fatigue	175	20% (8%) 7%	Anorexia/Weight Loss	15	(<1%) 2%
Cystitis Urgency	134	(0) 6% (2%) 6%	Urinary Debris Allergy	15	(<1%) 2%
Nocturia	50 40	(1%) 5% (1%)	Cardiac (Unclassified)	15	(<1%) 2%
Cramps/Pain	39 30	4% (1%) 3%	Genital Inflammation/ Abscess	14	(<1%) 2%
Rigors	27 22	(1%) 3% (<1%)	Respiratory (Unclassified)	13	(1%) 2%
Nausea/Vomiting	20		Urinary Tract Infection	12	(<1%) 2%
			Abdominal Pain	11	(<1%) 2%
				10	(1%) 2%
				10	(1%)

The following adverse events were reported in $\leq 1\%$ of patients: anemia, BCG sepsis, coagulopathy, contracted bladder, diarrhea, epididymitis/prostatitis, hepatic granuloma, hepatitis, leukopenia, neurologic (unclassified), orchitis, pneumonitis, pyuria, rash, thrombocytopenia, urethritis, and urinary obstruction.

In SWOG study 8795, toxicity evaluations were available on a total of 222 TICE® BCG-treated patients and 220 MMC-treated patients. Direct bladder toxicity (cramps, dysuria, frequency, urgency, hematuria, hemorrhagic cystitis, or incontinence) was seen more often with TICE® BCG, with 356 events compared to 234 events for MMC. Grade ≤ 2 toxicity was seen significantly more frequently following TICE® BCG treatment ($p=0.003$). No life-threatening toxicity was seen in either arm. Systemic toxicity with TICE® BCG was markedly increased compared to that of MMC, with 181 events for TICE® BCG compared to 80 for MMC. The frequency of toxicity was increased in all grades, particularly for grades 2 and 3. The most common complaints were malaise, fatigue and lethargy, fever, and abdominal pain. Thirty-two TICE® BCG patients were reported to have been treated with isoniazid. Five TICE® BCG patients had liver enzyme elevation, including two with grade 3 elevations. Eighteen of the 222 (8.1%) TICE® BCG patients failed to complete the prescribed protocol compared to 6.2% in the MMC group.

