15.4.2 Procedure for Protecting Against or Minimizing any Potential Risks

All care will be taken to minimize side effects, but they can be unpredictable in nature and severity. This study may involve risks to patients, which are currently unforeseeable. All patients will have blood tests, examinations and CT scans of the chest/abdomen/pelvis as described in the monitoring schedule as described in Appendix C (Section 17.3). Patients will also be required to have a local physician to provide long-term care and to monitor for complications. If patients suffer any physical injury as a result of the participation in this study, immediate medical treatment is available at the Warren Grant Magnuson Clinical Center, Bethesda, Maryland. Although no compensation is available, any injury will be evaluated and

treated in keeping with the benefits or care to which patients are entitled under applicable regulations.

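### Blood safety tests are scheduled only at baseline and week 17-20, so blood-based safety triggers depend on unscheduled testing and laboratory grades are not ascertained alike in the two arms

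*Combined protocol and SAP*

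**What the plan says.** **Schedule.** In calendars A and B of Section 11, the rows "CBC with differential", chemistry and PT/PTT each have a mark at baseline, a mark at week 17-20 and an optional mark in follow-up. None is marked at weeks 0, 3 to 8, 11 or 15. A calendar footnote adds: "Baseline laboratory studies should be completed within 28 days of initiating treatment". Blood drawn on treatment (weeks 0, 3 and 8 in both arms, also 11 and 15 in the combination arm) is for immunologic research. Sections 3.4, 5.2, 6.2 and 10.1 and the safety visit in 5.8 add no on-treatment blood count or chemistry.

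**Rules and statements that need a laboratory result.**
- 10.1.5: "Serum for NCA (CEA-CAM) titers will be drawn anytime that a patient exhibits new onset neutropenia (ANC <1000".
- 5.4: a DLT is a grade 3 or higher CTCAE event "related to the investigational agent and persisting for more than one week and not improving by routine standard of care". Laboratory terms are not excluded.
- 6.2.1: vaccination ends if vaccine-attributable nonautoimmune toxicity of grade 2 or more lasts over 42 days, and the patient leaves protocol treatment for any attributable grade 4 toxicity. Vaccine is also held for more than "grade 2 proteinuria measured initially by a urine dipstick but confirmed by a 24 hour urine collection".
- 8.1.1.1 lists anemia and raised ALT as possibly vaccine-related, and its notes say: "Thrombotic thrombocytopenic purpura (TTP) occurred with closely related agents".
- 15.4.3 says that laboratory data are collected often.

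**Use of the data.** Section 13.1 follows adverse events until 30 days after study treatment ends, or until off-study if sooner. Section 14.2 compares toxicity grades between arms with Fisher's exact test.

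**The concern.** The protocol has rules that act on laboratory values during dosing, but the calendars measure no blood safety value during dosing. An abnormality that causes no symptoms would be seen only if someone ordered a test outside the schedule. Safety of the combination is a stated secondary objective (1.2.2), so an absence of laboratory DLTs could reflect an absence of measurement.

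There is also a statistical consequence. The arms finish study treatment seven weeks apart but share the same single post-baseline draw. A window tied to the last dose then treats that draw differently by arm.

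**Working it through.** **1. Scheduled blood safety tests during dosing.** From the Section 11 rows, the number of CBC, chemistry or PT/PTT marks between baseline and week 17-20 is 0 in each arm. Doses given before week 17 on the nominal schedule (5.1):
- combination arm: 1 vaccinia + 4 fowlpox + 6 BCG = 11
- BCG-alone arm: 6 BCG

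**2. Length of the gap.** Baseline tests may be 28 days (4 weeks) before treatment starts.
- Combination arm, first dose at week 0: (17 to 20) + 4 = 21 to 24 weeks at most.
- BCG-alone arm, first dose at week 3: (17 to 20) − 3 + 4 = 18 to 21 weeks at most.

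The week 17-20 draw falls 17 − 8 = 9 to 20 − 8 = 12 weeks after the nominal last BCG dose, and 17 − 15 = 2 to 20 − 15 = 5 weeks after the nominal last vaccine dose.

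**3. Proteinuria hold.** Boosters are given at weeks 3, 7, 11 and 15. Calendar A marks urinalysis at weeks 3 to 8, 15 and 17-20. The hold therefore has a scheduled measurement at three boosters and none at week 11. This assumes that the scheduled urinalysis reports protein.

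**4. Adverse event window.** Window end = last dose + 30/7 weeks, and 30/7 = 4.3.
- BCG alone: 8 + 4.3 = week 12.3. The draw at week 17-20 is wholly outside.
- Combination: 15 + 4.3 = week 19.3. The draw is inside from week 17 to 19.3, which is 2.3 of the 3 weeks.

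BCG postponements do not easily change the first result. Even a last BCG dose at week 12, four weeks late, gives 12 + 4.3 = 16.3, still before week 17.

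Toxicity counts from first treatment (12.1.1.1). The windows therefore run from week 3 to 12.3 (9.3 weeks) with BCG alone and from week 0 to 19.3 (19.3 weeks) with the combination. The longer window, and the only scheduled laboratory result within a window, belong to the combination arm. If the window is applied, laboratory grades are tilted against the combination. No size can be given, because the documents state no laboratory toxicity rate for it.

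**5. Blood volume.** Scheduled research blood in the combination arm over weeks 0 to 8 (10.1.3): (10 + 60 + 20) + 80 + 80 = 250 mL. The limit is 550 mL or 10.5 mL/kg, whichever is smaller; the weight limit governs below 550/10.5 = 52.4 kg.

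**6. The plan's own safety figure, as context.** Section 14.1 states stopping probabilities of 0.04 at a 6% event rate and 0.94 at 30%. An exact sequential binomial calculation over 26 patients gives 0.0345 and 0.939, so the stated figures reproduce. They take events as observed, and the point here does not rest on them.

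**The case against.** The scheduling fact is hard to dispute, so the case on the other side concerns what follows from it. Several stronger readings are tempting, and the documents do not support them.

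- **That the laboratory rules cannot operate.** Prompted tests are not barred. History and physical is scheduled at each treatment visit from week 3, apart from week 11 with BCG alone, when nothing is given. Section 13.1 lets symptomatic, treated or investigator-judged abnormalities count as adverse events. Urinalysis before each BCG dose supports the hematuria and infection hold, and three of four boosters have one for the proteinuria hold. The neutropenia trigger leads to a serum titer and changes no dose.
- **That DLT persistence needs a second scheduled draw.** Section 13.1 follows clinically significant laboratory findings until return to baseline or stabilization, so a detected abnormality would be rechecked. The gap is in first detection.
- **That the stopping rule misses most laboratory events.** The table in 14.1 counts serious grade 3 or 4 events, and 5.4.2 requires persistence beyond a week. Brief silent abnormalities mostly fall outside it by definition, and the documents give no share missed.
- **That a count of missed liver events follows from 8.1.2.1.** The text reads "Five TICE® BCG patients had liver enzyme elevation, including two with grade 3 elevations". Five of 222 covers all grades. At grade 3 the rate is 2/222 = 0.9%, or about 0.5 patients in 54, and it describes BCG alone.
- **That no scheduled result could ever affect a dose.** Section 6.2.1 allows a non-toxicity vaccine delay of up to 42 days, so the last booster could fall at week 15 + 6 = 21, after the draw.
- **That the Appendix C reference proves a missing schedule.** Section 15.4.2 describes blood tests "as described in the monitoring schedule as described in Appendix C", which is titled a patient instruction sheet. I have not seen the body of that appendix, so this is a cross-reference to check and no more.

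The protocol also halts accrual for 28 days after the first six combination patients and cites earlier experience with these vectors. That helps to explain light monitoring, but it does not supply a measurement for the rules that need one.

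**Conclusion.** The point holds in a limited form. No CBC, chemistry or PT/PTT is scheduled from baseline until after all nominal dosing, a gap of up to 24 weeks and 11 doses in the combination arm. Blood-based triggers therefore depend on unscheduled, mainly symptom-prompted testing. Asymptomatic laboratory toxicity during dosing would go undetected, which does not fit the statement in 15.4.3. One of four boosters, week 11, has no scheduled urinalysis for the proteinuria hold. If the 30-day window is applied as written, the only post-baseline draw counts mostly in one arm and not in the other.

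This rests on the nominal schedule and on the calendar marks standing in the columns where they appear. The urinalysis row of calendar A deserves a look at the source table: it has no follow-up mark, although the footnote on follow-up includes urinalysis. With only two marks after week 8, one of them at week 17-20, at most one of the week 11 and week 15 boosters can be covered on any reading.

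It should be corrected, but it does not invalidate the design. The number of events missed cannot be estimated from the documents.

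**What to change.** 1. Reconcile the Section 11 calendars with 5.4, 6.2.1, 10.1.5 and 15.4.3, so that each laboratory-dependent rule has its measurement at a visit where it acts. Blood is already drawn at weeks 3 and 8 in both arms and at weeks 11 and 15 in the combination arm. Resolve the week 11 urinalysis gap against 6.2.1. Which tests are done when, and what is done with a result, are for the clinical team to decide.
2. In 14.2, compare laboratory grades only over time points and an adverse event window common to both arms. On the present calendar the only common scheduled post-baseline point is week 17-20, and a common window closing at week 12.3 contains no scheduled draw. The plan must therefore say whether week 17-20 results count in both arms whatever the 30-day limit. Any tests added in one arm only should stay out of the between-arm comparison.
3. Do not report an absence of laboratory DLTs as measured safety for periods in which no test was scheduled. If dosing has finished, steps 2 and 3 can still be taken.
4. Check the Appendix C reference in 15.4.2.

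The cost is small: laboratory charges and a little blood at visits that already draw 80 mL, with the lower volume limit to be watched in patients under 52.4 kg, plus one urine test. Steps 2 to 4 need only text.
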